## 1. LIST OF ABBREVIATIONS

Abbreviation	Definition
AIDS	Acquired immune deficiency syndrome
CABG	Coronary Artery Bypass Graft surgery
CHA 2 DS 2 -VASc	Clinical stroke risk prediction tool based on comorbidities of congestive heart failure, hypertension, elderly age, diabetes mellitus, prior stroke or thromboembolism, vascular disease, and gender.
HAS-BLED	Clinical major bleeding risk score based on comorbidities of hypertension, abnormal renal and liver function, prior stroke, bleeding history, labile international normalized ratio values of anticoagulation level, elderly age, and concomitant drug or alcohol use.
HIRA	Health Insurance Review & Assessment Service
HIV	Human immunodeficiency virus
ICD-10	International Classification of Diseases 10 th revision
ICJME	International Committee of Medical Journal Editors
KCD-6	Korean Standard Classification of Diseases 6 th revision
KCD-7	Korean Standard Classification of Diseases 7 th revision
MI	Myocardial infarction
MPR	Medication possession ratio
NOAC	Non vitamin K antagonist oral anticoagulants
NSAIDs	Nonsteroidal anti-inflammatory drugs
NVAF	Nonvalvular atrial fibrillation
OAC	Oral anticoagulants
PCI	Percutaneous coronary intervention

Abbreviation	Definition
PPI	Proton pump inhibitor
TE	Thromboembolism
TIA	Transient ischemic attack

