### 8.2.2 Exclusion criteria

Patients meeting any of the following criteria will not be included in the study.

1. Medical claims indicating diagnosis or procedure for hip/knee replacement surgery within 6 weeks prior to index date
2. Medical claims indicating a diagnosis code indicative of rheumatic mitral valvular heart disease, mitral valve stenosis during the 12-month baseline period  
(Valvular AF / Prosthetic heart valves)
3. Medical claims indicating a diagnosis code of VTE (Venous thromboembolism) during the 12-month baseline period
4. Medical claims indicating a diagnosis or procedure code of transient AF, or cardiac surgery during the 12-month baseline period

(Thyrotoxicosis, Hypertrophic cardiomyopathy, Elective defibrillation, radiofrequency ablation, or left atrial appendage occlusion)

5. Medical claims indicating a diagnosis code of other conditions during the 12-month baseline period  
(End-stage chronic kidney disease / Kidney transplant / Dialysis / Pericarditis)
6. For the comparison of “NOAC versus NOAC”, and “NOAC versus warfarin”, patients with any OACs (apixaban, dabigatran, rivaroxaban, or warfarin) in the pre-index period (from 1 year prior to the day before index date)
  - *[NOTE] Patients prescribed antiplatelets in the pre-index period will not be excluded.*
7. For the comparison of “NOAC versus aspirin”, patients with following medications in the pre-index period (from 1 year prior to the day before index date)
  - NOAC user: OACs (apixaban, dabigatran, rivaroxaban, warfarin)
  - Aspirin user: none
  - *[NOTE] NOAC user is defined as OAC naïve user and aspirin user is allowed to have OACs or antiplatelets in the pre-index period.*

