Exclusion criteria	Exclusion criteria	HIRA database	
Claims with the following KCD codes or procedure codes:
 
 
1. Valvular AF/ Prosthetic heart valves: I05, I08, I09, I34, Q23, T820, T826, Z952, Z953, Z954            - Korean procedure codes: M6580, M6581, M6582, O1791, O1792, O1793, O1794, O1795, O1796, O1797, O1798, O1799, M6531, M6532, M6533, O1690, O1730, 1740, O1750, O1760, O1770, O1781, O1782, O1783, O1810, O1826
 
2. End-stage of chronic kidney disease/dialysis: N185, T824, Y602, Y612, Y622, Y841, Z49, Z992, E1022, E1122, E1222, E1322, E1422
 
3. Kidney transplant: Z940
 
4. Venous thromboembolism: I636, I676, I801, I802, I803, I808, I809, I81, I822, I823, I829, I26
 
5. Hip or knee replacement            - Korean procedure codes: N0711, N0715, N1711, N1715, N1721, N1725, N2070, N2072, N2077, N2710, N2712, N2717, N3710, N3712, N3717, N3720, N3722, N3727, N4710, N4712, N4717, N4720, N4722, N4727
 
6. Thyrotoxicosis: E05
 
7. Pericarditis: I30, I31, I32
 
8. Hypertrophic cardiomyopathy: I422
 
9. Elective defibrillation, radiofrequency ablation, or left atrial appendage occlusion            - Korean procedure codes: M5880, M6540, M6542, M6545, M6547, M6511
 

Follow-up period	Follow-up period	HIRA database	
From the index date until the first occurrence of the following whichever came first:
 
 
1. Discontinuation: maximum of a 30-day gap after the calculated time to finishing the pack based on pack size and number of tablets per day. Switching: switch to any other study drugs
 
2. Outcome occurrence
 
3. Study ends: November 30, 2016
 

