3 ANALYSIS SETS/ POPULATIONS

3.1 FULL ANALYSIS SET

Inclusion criteria

Patients must meet all of the following inclusion criteria to be eligible for inclusion in the study:

1. Patients aged 18 years or older on the index date
2. Patients had ≥ 1 medical claim for AF (refer to Table 1) before or on the index date with at least one hospitalization or at least two outpatient visits:

[Diagnosis codes for inclusion criteria]

KCD-6 ¹⁾	KCD-7 ²⁾
I48 (Atrial fibrillation and flutter)	I48 (Atrial fibrillation and flutter)
I480 (Atrial fibrillation)	I480 (Paroxysmal atrial fibrillation)
I481 (Atrial flutter)	I481 (Persistent atrial fibrillation)
	I482 (Chronic atrial fibrillation)
	I483 (Typical atrial flutter)
	I484 (Atypical atrial flutter)
	I489 (Atrial fibrillation and atrial flutter, unspecified)

KCD-6, Korean version of ICD-10 (6th revision); KCD-7, Korean version of ICD-10 (7th revision)

1) KCD-6 diagnosis codes will be used from 1 July 2015 to 31 December 2015.

2) KCD-7 diagnosis codes will be used from 1 January 2016 to 30 November 2016.

[NOTE] KCD code is based on ICD-10 and almost similar, but KCD code is slightly different from ICD-10 (e.g., ICD-10 is more subdivided and extensive than KCD code).

3. Patients prescribed aspirin, warfarin, or NOACs in intake period (from July 1, 2015 to November 30, 2016)
[Note] NOACs include apixaban, dabigatran and rivaroxaban.

Exclusion criteria

Patients meeting any of the following criteria will not be included in the study.

1. Medical claims indicating diagnosis or procedure for hip/knee replacement surgery within 6 weeks prior to index date
2. Medical claims indicating a diagnosis code indicative of rheumatic mitral valvular heart disease, mitral valve stenosis during the 12-month baseline period
(Valvular AF / Prosthetic heart valves)
3. Medical claims indicating a diagnosis code of VTE (Venous thromboembolism) during the 12-month baseline period
4. Medical claims indicating a diagnosis or procedure code of transient AF, or cardiac surgery during the 12-month baseline period
(Thyrotoxicosis, Hypertrophic cardiomyopathy, elective defibrillation, radiofrequency ablation, or left atrial appendage occlusion)
5. Medical claims indicating a diagnosis code of others during the 12-month baseline period
 - (End-stage chronic kidney disease / Kidney transplant / Dialysis / Pericarditis)

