Hip or knee replacement*	N0711, N0715, N1711, N1715, N1721, N1725, N2070, N2072, N2077, N2710, N2712, N2717, N3710, N3712, N3717, N3720, N3722, N3727, N4710, N4712, N4717, N4720, N4722, N4727
Elective defibrillation/ radiofrequency ablation/ left atrial appendage occlusion*	M5880, M6540, M6542, M6545, M6547, M6511

[*Note] Hip or knee replacement, elective defibrillation, radiofrequency ablation, and left atrial appendage occlusion will be identified using procedure codes.

Table 14. Blood Transfusion Codes

Condition	Korean procedure code
Whole Blood	X1001
Whole Blood	X1002
Fresh Liquid Plasma for Whole Blood 320ml	X2011
Fresh Liquid Plasma for Whole Blood 400ml	X2012
Packed RBC for Whole Blood 320ml	X2021
Packed RBC for Whole Blood 400ml	X2022
Washed RBC for Whole Blood 320ml	X2031
Washed RBC for Whole Blood 400ml	X2032
Fresh Frozen Plasma for Whole Blood 320ml	X2041
Fresh Frozen Plasma for Whole Blood 400ml	X2042
Frozen Plasma for Whole Blood 320ml	X2051
Frozen Plasma for Whole Blood 400ml	X2052
Cryoprecipitate for Whole Blood 320ml	X2061
Cryoprecipitate for Whole Blood 400ml	X2062
Platelet rich plasma for whole blood 320ml	X2071

NIS Protocol <X9001134>
Statistical Analysis Plan
<Version 3.0> <03 May 2018>

Condition	Korean procedure code
Platelet Rich Plasma for Whole Blood 400ml	X2072
Platelet Concentrate for Whole Blood 320ml	X2081
Platelet Concentrate for Whole Blood 400ml	X2082
Leukocyte Poor Packed RBC for Whole Blood 320ml	X2091
Leukocyte Poor Packed RBC for Whole Blood 400ml	X2092
Packed WBC for Whole Blood 320ml	X2101
Packed WBC for Whole Blood 400ml	X2102
Leukocyte Filtered Packed RBC for Whole Blood 320ml	X2111
Leukocyte Filtered Packed RBC for Whole Blood 400 ml	X2112
Leukocyte Filtered Packed Platelet Concentrate for Whole Blood 320ml	X2121
Leukocyte Filtered Packed Platelet Concentrate for Whole Blood 400ml	X2122
Red Blood Cells, Cryopreserved and Thawed for Whole blood 320ml	X2131
Red Blood Cells, Cryopreserved and Thawed for Whole blood 400ml	X2132
Plasma, Cryoprecipitate Reduced for Whole blood 320ml	X2141
Plasma, Cryoprecipitate Reduced for Whole blood 400ml	X2142
Fresh Blood	X3010

NIS Protocol <X9001134>
Statistical Analysis Plan
<Version 3.0> <03 May 2018>

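### Exclusion 4 names cardiac surgery, but neither its bracket nor the code lists put that into effect beyond the valve row, so patients with recent bypass or other non-valve heart surgery stay in the cohort

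*Protocol*

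**What the plan says.** Protocol 8.2.2, item 4, excludes patients with "Medical claims indicating a diagnosis or procedure code of transient AF, or cardiac surgery during the 12-month baseline period". SAP 3.1 repeats it: "diagnosis or procedure code of transient AF, or cardiac surgery during the 12-month baseline period".

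The bracket directly under the Protocol item reads "Thyrotoxicosis, Hypertrophic cardiomyopathy, Elective defibrillation, radiofrequency ablation, or left atrial appendage occlusion". The SAP has the same five items.

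The operative codes are in the exclusion row of Protocol 8.3 and in SAP Table 13. For the items in the bracket they give E05 (thyrotoxicosis), I422 (hypertrophic cardiomyopathy) and one procedure row, labelled "Elective defibrillation, radiofrequency ablation, or left atrial appendage occlusion" in the Protocol, with six codes: "M5880, M6540, M6542, M6545, M6547, M6511".

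Other heart procedures appear only in the row that begins "Valvular AF/ Prosthetic heart valves: I05, I08, I09, I34, Q23, T820, T826, Z952, Z953, Z954" and continues with a list of procedure codes. That row serves exclusion 2. No row in either document is labelled cardiac surgery, bypass or coronary surgery.

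**The concern.** A programmer works from the code table. If the table has no entry for a condition that the criterion names, that part of the criterion is not applied, and a report that repeats the criterion describes a cohort that was not built.

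The gap matters here because item 4 is the plan's safeguard against transient AF. The AF criterion (Protocol 8.2.1, item 2) is met by a single hospitalization with an AF code, at any time from January 2007 up to the index date, and nothing requires the AF to persist. AF recorded during a heart-surgery admission is enough. The surgical part of item 4 is the only rule aimed at such patients, and as coded it reaches none of them outside the valve row. This affects who counts as an NVAF patient in all nine sub-datasets, and it could bias a comparison if the affected patients are unevenly spread between its arms.

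**Working it through.** The plan states no figure on this point, so there is nothing to reproduce. The check sets the text against the codes, then illustrates the size.

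**1. Criterion, bracket and codes**

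| Element of item 4 | In the bracket? | Codes (Protocol 8.3 and SAP Table 13) |
|---|---|---|
| Thyrotoxicosis | yes | E05 |
| Hypertrophic cardiomyopathy | yes | I422 |
| Defibrillation, ablation, appendage occlusion | yes | six procedure codes, the same in both documents |
| Cardiac surgery | no | none |

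The valve row has 36 codes (10 diagnosis, 26 procedure) and is identical in the two documents. The remaining rows are end-stage kidney disease and dialysis, kidney transplant, venous thromboembolism, hip or knee replacement, and pericarditis.

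This comparison rests on row labels. The procedure codes have no individual descriptions, and the documents do not say whether the ablation and appendage codes are surgical or catheter procedures.

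**2. What happens to a patient with recent isolated bypass surgery.** Suppose AF is coded during the surgical admission and a study drug is first prescribed in the intake period. The AF criterion is met. Item 4 as coded does not remove the patient. Another exclusion may do so by chance: a valve, pericarditis or venous thromboembolism code, or prior anticoagulant use in a NOAC or warfarin user. Otherwise the patient enters as NVAF.

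**3. Whether later adjustment is assured.** It is not.
- Prior cardiac surgery is neither a covariate in SAP Table 4 nor a row in the Table 5 shell.
- The vascular codes in CHA₂DS₂-VASc (SAP Table 9) are I21, I252 and I70-I73, with no procedure code.
- Coronary disease is in the Table 5 shell but has no code list.
- SAP 5.1 leaves the final propensity-score covariates open.

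**4. Illustrative size in NOAC versus aspirin (sub-datasets 7-9).** All inputs are assumptions, because the documents give no counts by arm. Let p1 and p0 be the shares with recent non-valve heart surgery in the aspirin and NOAC arms, and RR their outcome risk relative to the other patients.

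Crude bias factor on the aspirin-to-NOAC rate ratio = [1 + p1(RR − 1)] / [1 + p0(RR − 1)]

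| p1 | p0 | RR = 0.7 | RR = 2 |
|---|---|---|---|
| 1% | 1% | 1.000 | 1.000 |
| 1% | 0.2% | 0.998 | 1.008 |
| 3% | 1% | 0.994 | 1.020 |
| 3% | 0.2% | 0.992 | 1.028 |
| 5% | 1% | 0.988 | 1.040 |
| 5% | 0.2% | 0.986 | 1.048 |

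The extremes in full:
- Lowest: (1 − 0.05 × 0.3) / (1 − 0.002 × 0.3) = 0.985 / 0.9994 = 0.986
- Highest: 1.05 / 1.002 = 1.048

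With RR = 3 the last row gives 1.10 / 1.004 = 1.096.

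The NOAC-versus-aspirin HR is divided by this factor. An illustrative true HR of 0.80 would be seen as 0.80 / 0.986 = 0.81 or 0.80 / 1.048 = 0.76 at the two ends, before any propensity-score adjustment.

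**The case against.** **The bracket may be the whole definition.** Items 2 and 5 have the same form, with general words followed by a bracket that names what is coded. Read that way, the codes match item 4 exactly, and the fault is a heading wider than its content rather than a planned bypass exclusion that fails to run. This reading is open. It does not remove the problem, because the criterion still announces an exclusion that is not applied. It does change which correction is right, so the fix allows for both readings.

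**The abbreviation list proves little.** It contains "Coronary Artery Bypass Graft surgery", but no criterion uses the term. The SAP's amendment log records that an objective on coronary intervention patients was moved to a separate protocol, so the entry may be left over from that. The point rests on the wording of item 4 alone.

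**Adjustment may absorb much of the imbalance.** Matching and weighting are planned with a standardized-difference limit of 0.1. The Charlson and CHA₂DS₂-VASc scores are named covariates, and infarction, coronary disease and antiplatelet use are in the baseline shell. This is fair, and it is why the figures above are called crude. Adjustment is likely to help but is not guaranteed while the covariate list is open.

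**A stronger reading that the documents do not support.** A reader might infer that these patients gather in the aspirin arm and make aspirin look better on stroke. If 3-8% of the aspirin arm and none of the NOAC arm were such patients, with half the stroke rate, the aspirin rate would be multiplied by 1 − 0.5 × 0.03 = 0.985 to 1 − 0.5 × 0.08 = 0.96, and an HR of 0.80 would become 0.81 to 0.83. All three inputs are unsourced, and zero in the NOAC arm is the extreme case. Aspirin users have no pre-index drug restriction, which makes an imbalance plausible, but antiplatelet use before index is allowed in every arm. Patients with coronary disease could also have a higher stroke rate, which would reverse the direction.

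**Conclusion.** The mismatch is real and can be verified on the page: both documents state a cardiac-surgery exclusion, and neither gives a code for it outside the valve row. As coded, patients with recent bypass or other non-valve heart surgery remain unless another exclusion applies, and AF from one surgical admission can qualify them in any sub-dataset.

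The effect on the hazard ratios is not established. Over the assumed range the crude factor runs from about 0.99 to 1.05. It crosses 1, and it equals 1 when the shares are the same in both arms. Neither clustering in the aspirin arm nor a direction of bias can be claimed from these documents. The case for acting is that the plan does not deliver a rule it states, that this rule protects the NVAF definition, and that an expected cohort of about 150,000 does nothing to reduce a systematic error.

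**What to change.** Reconcile item 4 in Protocol 8.2.2 and SAP 3.1 with the code lists.

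- **Preferred:** add a cardiac-surgery row to Protocol 8.3 and SAP Table 13, holding the Korean procedure codes for coronary bypass and other open-heart operations, applied over the same 12-month window, and name it in the bracket. This delivers the exclusion as written.
- **If the bracket is meant as the full definition:** narrow the wording of item 4 to the coded items, add prior cardiac surgery by arm to the SAP Table 5 shell, and include it in the propensity score.

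Both routes need the same codes, so narrowing the wording does not save the look-up. The codes are not in the documents and must come from the Korean procedure code schedule. No new data request is needed, since Protocol 8.6 already covers all claims from January 2007 to November 2016. The cost is one code row in each document and, on the preferred route, slightly fewer patients.

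One limit remains on either route: AF recorded at an operation before the 12-month window would still qualify a patient, because the AF look-back reaches to 2007.

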#### ***Secondary objectives***

1. To explore and understand more detailed drug utilization patterns
  - o Standard doses versus reduced doses of NOACs

- Patterns of usage (i.e., switching, discontinuation) and clinical events preceding the pattern
- Compliance (i.e., medication possession ratio)

2. To compare effectiveness and safety of antithrombotic therapies versus not using therapies among low risk patients (low score of CHA2DS2-VASc)

**Study design:** Retrospective cohort study

**Population:** Subjects with atrial fibrillation diagnosed (from January 1, 2007 up to and including the index date\*) who newly initiated antithrombotic therapies (NOACs (not including edoxaban), warfarin, or used aspirin) between July 1, 2015 and November 30, 2016 in the Korean Health Insurance Review & Assessment Service (HIRA) database

*\*Index date is the first prescription date of study drugs, including NOACs, warfarin, and aspirin during the intake period (from July 1, 2015 to November 30, 2016).*

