**Table 1. Diagnosis codes for inclusion criteria.**

KCD-6 	KCD-7 
I48 (Atrial fibrillation and flutter)	I48 (Atrial fibrillation and flutter)
I480 (Atrial fibrillation)	I480 (Paroxysmal atrial fibrillation)
I481 (Atrial flutter)	I481 (Persistent atrial fibrillation)
	I482 (Chronic atrial fibrillation)
	I483 (Typical atrial flutter)
	I484 (Atypical atrial flutter)
	I489 (Atrial fibrillation and atrial flutter, unspecified)

KCD-6, Korean version of ICD-10 (6th revision); KCD-7, Korean version of ICD-10 (7th revision)

1) KCD-6 diagnosis codes will be used from 1 July 2015 to 31 December 2015.

2) KCD-7 diagnosis codes will be used from 1 January 2016 to 30 November 2016.

[NOTE] KCD code is based on ICD-10 and almost similar, but KCD code is slightly different from ICD-10 (e.g., ICD-10 is more subdivided and extensive than KCD code).

3. Patients prescribed aspirin, warfarin, or NOACs during intake period (from July 1, 2015 to November 30, 2016)

*[Note] NOACs include apixaban, dabigatran, and rivaroxaban.*

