## 8.5 Study size

Based on the 2015-2016 HIRA disease statistics, there are 148,130 – 169,259 patients with atrial fibrillation (KCD code: I48). Thus, we anticipate getting the number of patients with approximately 150,000 since we plan to include patients who already had atrial fibrillation and were prescribed aspirin, warfarin, or NOACs from July 1, 2015 to November 30, 2016. However, the study size might change after applying inclusion and exclusion criteria.

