2.2 STUDY OBJECTIVES

Primary objectives

1. To explore baseline characteristics and drug utilization patterns in patients with nonvalvular atrial fibrillation (NVAF) who newly initiated NOACs, warfarin, or used aspirin
 - Demographic and clinical characteristics: Age, sex, types of health insurance, CHA₂DS₂-VASc score, HAS-BLED score, Charlson Comorbidity Index score, etc.
 - Descriptions of index treatment: Types of medication received, index dose intensity
 - Drug utilization pattern: Each patient will be followed-up until the first treatment modification occurs, or study ends (November 30, 2016).
2. To compare effectiveness including hemorrhagic stroke, ischemic stroke and systemic embolism of antithrombotic therapies in patients with NVAF with the following antithrombotic therapies: NOACs, warfarin, and aspirin
 - Primary effectiveness outcome: Composite of hemorrhagic stroke, ischemic stroke, and systemic embolism
 - Secondary effectiveness outcomes: Individual outcome of hemorrhagic stroke, ischemic stroke, and systemic embolism
3. To compare safety of anti-thrombotic therapies in patients with NVAF with the following antithrombotic therapies: NOACs, warfarin, and aspirin
 - Primary safety outcome: Major bleeding including gastrointestinal bleeding or intracranial bleeding and other bleeding
 - Secondary safety outcomes: Individual outcome of major bleeding

[NOTE] comparative analyses will be performed contingent on a feasibility assessment based on the descriptive analyses.

Secondary objectives

1. To explore and understand more detailed drug utilization patterns
 - Standard dose versus reduced dose

- Pattern of usage (i.e., switching, discontinuation) and clinical events preceding the pattern
- Compliance (i.e., medication possession ratio)

2. To compare effectiveness and safety of antithrombotic therapies versus not using therapies among low risk patients (low score of CHA₂DS₂-VASc)

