6. For the comparison of “NOAC versus NOAC”, and “NOAC versus warfarin”, patients with any OACs (apixaban, dabigatran, rivaroxaban, or warfarin) in the pre-index period (from 1 year prior to the day before index date)
 - *[NOTE] Patients prescribed antiplatelets in the pre-index period will not be excluded.*
7. For the comparison of “NOAC versus aspirin”, patients with following medications in the pre-index period (from 1 year prior to the day before index date)
 - NOAC user: OACs (apixaban, dabigatran, rivaroxaban, warfarin)
 - Aspirin user: none
 - *[NOTE] NOAC user is defined as OAC naïve user and aspirin user is allowed to have OACs or antiplatelets in the pre-index period.*

Cohorts

To avoid increasing type I error when multiple comparisons occur, this full analysis set will be splitted into multiple sub-analysis sets as follows:

1. NOAC vs NOAC (both as OAC naïve users)
 - A. Sub-dataset 1: patients with index treatment of apixaban and patients with index treatment of dabigatran
 - B. Sub-dataset 2: patients with index treatment of apixaban and patients with index treatment of rivaroxaban
 - C. Sub-dataset 3: patients with index treatment of dabigatran and patients with index treatment of rivaroxaban

[NOTE] The index date will be defined as date of the first prescription of NOAC in patients with NVAF. To identify new users, a look-back observation period from 1 year prior to the day before the index date will be used and must indicate no OAC use during this period. The diagnosis date of NVAF could occur from January 1, 2007 up to and including the index date.

2. NOAC vs warfarin (both as OAC naïve users)
 - A. Sub-dataset 4: patients with index treatment of apixaban and patients with index treatment of warfarin
 - B. Sub-dataset 5: patients with index treatment of dabigatran and patients with index treatment of warfarin
 - C. Sub-dataset 6: patients with index treatment of rivaroxaban and patients with index treatment of warfarin

[NOTE] The index date will be defined as date of the first prescription of NOAC or warfarin in patients with NVAF. To identify new users, a look-back observation period from 1 year prior to the day before the index date will be used and must indicate no OAC use during this period. The diagnosis date of NVAF could occur from January 1, 2007 up to and including the index date.

3. NOAC (OAC naïve user) vs aspirin (no restrictions of antiplatelet or OAC use in the pre-index period)

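### Primary objective 1 describes new NOAC and warfarin initiators, but the one-year OAC-free look-back is written only for the pairwise comparisons, so long-term users can enter the descriptive analyses

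*Protocol*

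**What the plan says.** Primary objective 1 (Protocol 7; SAP 2.2) reads: "To explore baseline characteristics and drug utilization patterns in patients with nonvalvular atrial fibrillation (NVAF) who newly initiated NOACs, warfarin, or used aspirin". The population statements in the Protocol abstract and SAP 2.1 describe the patients in the same way, with no washout length attached.

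The operational rules are these:

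- Inclusion criterion 3 (Protocol 8.2.1, repeated in substance in SAP 3.1): "Patients prescribed aspirin, warfarin, or NOACs during intake period (from July 1, 2015 to November 30, 2016").
- Index date (Protocol abstract, Population): "Index date is the first prescription date of study drugs, including NOACs, warfarin, and aspirin during the intake period".
- Exclusions 1–5 (Protocol 8.2.2; SAP 3.1) concern joint replacement, valve disease, venous thromboembolism, transient AF or cardiac procedures, and renal disease or pericarditis. None mentions earlier anticoagulant use.
- Exclusion 6 carries the one-year OAC-free condition, and its scope is stated at the start: "For the comparison of “NOAC versus NOAC”, and “NOAC versus warfarin”, patients with any OACs (apixaban, dabigatran, rivaroxaban, or warfarin) in the pre-index period".
- Exclusion 7 covers NOAC versus aspirin only: "NOAC user is defined as OAC naïve user and aspirin user is allowed to have OACs or antiplatelets in the pre-index period".

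SAP 3.1 builds the full analysis set first and then says "this full analysis set will be splitted into multiple sub-analysis sets as follows". The look-back ("To identify new users, a look-back observation period from 1 year prior to the day before the index date will be used") appears in the notes under the NOAC–NOAC and NOAC–warfarin sub-datasets. An equivalent note covers the NOAC arm of the aspirin sub-datasets. Neither document names the analysis set for primary objective 1 or secondary objective 1.

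**The concern.** New use is the defining condition of primary objective 1 for NOAC and warfarin patients, yet no criterion for the descriptive set enforces it. A patient already established on treatment has passed the early period in which stopping and switching may be most common. Mixing such patients with starters changes what the baseline table, the index-treatment shares, discontinuation, switching and MPR describe: partly existing use rather than initiation.

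There is a second consequence. Both documents make the comparative analyses contingent on a feasibility assessment drawn from the descriptive analyses. If the descriptive counts include long-term anticoagulant users, feasibility is judged partly on patients whom exclusions 6 and 7 later remove. If the comparisons do not go ahead, the only written washout never comes into use.

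**Working it through.** **1. Trace one patient through the criteria.** Take a hypothetical adult with qualifying AF claims who has taken warfarin since 2010 and refills on 10 July 2015.

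| Rule | Result |
|---|---|
| Inclusion 1–2 (age, AF claims) | met |
| Inclusion 3 (prescription in intake) | met by the refill |
| Exclusions 1–5 | no OAC condition, so prior warfarin does not exclude |
| Exclusions 6–7 | apply only to the named comparisons |
| Protocol index date | 10 July 2015, if this is the first study-drug prescription in the window |

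The population label excludes this patient. The numbered criteria do not.

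**2. Could all the descriptive work use the washed-out sub-datasets?** SAP 5.1 tabulates index treatment over five groups: aspirin, clopidogrel, the aspirin–clopidogrel combination, warfarin and NOACs. Each of the nine sub-datasets holds two index drugs, and none holds clopidogrel or the combination. The five-group shares therefore cannot come from any sub-dataset. They need a wider set, to which exclusions 6 and 7 as worded do not apply. The definitions of discontinuation, switching and MPR in SAP Table 3 name no set.

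**3. The anticipated size.** Protocol 8.5 expects about 150,000 patients because "we plan to include patients who already had atrial fibrillation and were prescribed aspirin, warfarin, or NOACs from July 1, 2015 to November 30, 2016". Against its own AF counts:

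- 2015: 150,000 / 148,130 = 101.3%
- 2016: 150,000 / 169,259 = 88.6%

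The figure is on the scale of all coded AF, with no stated reduction for earlier OAC use. It is weak evidence: it is one total that includes aspirin users, whose prior OAC use is allowed, and the Protocol says it may change once the criteria are applied. It does not give the share of long-term OAC users.

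**4. Is the look-back possible?** Claims are requested from 1 January 2007, which is 3,103 days before intake opens on 1 July 2015. A one-year look-back is available for every index date.

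**5. Possible size (every rate and share here is assumed).** Let *s* be the share of established users, 45% the 12-month discontinuation in starters, and *p* that in established users (15–25%).

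Observed = (1 − *s*) × 45% + *s* × *p*; understatement = *s* × (45% − *p*).

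| *s* | Observed, *p* = 15% | Observed, *p* = 25% | Understatement (points) |
|---|---|---|---|
| 0 (label enforced) | 45% | 45% | 0 |
| 10% | 42% | 43% | 2–3 |
| 50% | 30% | 35% | 10–15 |
| 80% | 21% | 29% | 16–24 |

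**The case against.** The strongest reply is that both documents restrict the whole population to new initiators, so the patient in step 1 is outside the study on the plain words. The SAP also says how new users are identified, and a sensible programmer would carry that look-back over. Some description is evidently planned on washed-out data: SAP 5.1 refers to describing the pre-matched datasets, and the baseline shell (SAP Table 5) shows an apixaban–warfarin pair.

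Part of this stands. The label may be enforced in practice, and then the distortion is nil. But the label has no washout length, and the look-back that would supply one is tied to the comparisons. The reference to pre-matched datasets concerns the choice of propensity-score covariates, and the shell is marked as an example. Neither can account for the five-group shares.

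A reader might go further and infer that the descriptive set is full of long-term users, that they all enter in the first weeks of intake, or that persistence is misstated by a known amount, most of all for warfarin. The documents support none of these. They give no share of established users, overall or by drug, and no prescription lengths.

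**Conclusion.** The point holds as a mismatch between the stated population and the criteria meant to produce it, not as a demonstrated bias. As written, the criteria can admit long-term OAC users to the analyses for primary objective 1 and secondary objective 1. The direction is toward higher apparent persistence, provided that established users persist better than starters. The size is unknown: 0 to 24 percentage points of 12-month discontinuation over the assumed inputs, with the upper end needing an 80% share of established users and a 15% rate among them.

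The NOAC and warfarin arms of the pairwise effectiveness and safety comparisons are not affected, because exclusions 6 and 7 already require them to be OAC-free for a year. Aspirin is outside the point, since earlier use is expressly allowed there.

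**What to change.** In Protocol 8.2.2 and SAP 3.1, name the analysis set for primary objective 1 and secondary objective 1. State that its NOAC and warfarin patients must meet the existing one-year OAC-free look-back, and leave the aspirin rule as it is. If total current use is also of interest, report established users in a separate, labelled column.

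The cost is a few sentences in each document and a smaller descriptive set. The look-back is already specified for the comparisons (the documents do not say that it is programmed), and the claims history is already requested.

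One limit remains. The Protocol index date is the first prescription of any study drug in the window, including aspirin, so an aspirin refiller who later starts a NOAC is still indexed to aspirin. The index-treatment table should carry a note to that effect.
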